8.1. Efficacy Assessments

Not applicable.

8.2. Safety Assessments

Planned time points for all safety assessments are provided in the SoA.

8.2.1. Physical Examinations

A complete physical examination will include, at a minimum, assessments of the cardiovascular, respiratory, gastrointestinal, dermatological, and neurological systems. Height and weight will also be measured and recorded at screening.

Investigators should pay special attention to clinical signs related to COVID-19.

8.2.2. Vital Signs

For each participant, vital sign measurements should be conducted according to the SoA (Section 1.3). Additional vital signs may be measured during each study period at the investigator's judgment. Blood pressure and pulse rate should be measured after at least 5 minutes supine.

Orthostatic vital signs should be assessed, if possible, during any AE of dizziness or posture-induced symptoms. If orthostatic measurements are required, participants should be supine for at least 5 minutes and stand for at least 3 minutes. If the participant feels unable to stand, supine vital signs only will be recorded.

Additional vital signs may be measured during each study period, if warranted.

8.2.3. Electrocardiograms

A single, local, 12-lead ECG will be obtained as shown in the SoA, using an ECG machine that automatically calculates the heart rate and measures pulse rate, QRS, QT, and corrected QT intervals. Additional ECG readings may occur at investigator discretion.

8.2.4. Clinical Safety Laboratory Assessments

See Appendix 2 (Section 10.2) for the list of clinical laboratory tests to be performed and to the SoA for the timing and frequency.

All protocol-required laboratory assessments, as defined in Appendix 2, must be conducted in accordance with the laboratory manual and the SoA.

The investigator must review the laboratory report, document this review, and record any clinically relevant changes occurring during the study in the AE section of the CRF. The laboratory reports must be filed with the source documents.

If laboratory values from nonprotocol-specified laboratory assessments performed at the institution's local laboratory require a change in participant management or are considered clinically significant by the investigator (for example, SAE, AE, or dose modification), then the results must be recorded in the CRF.

8.2.5. Hepatic Monitoring

Close hepatic monitoring

In case of hepatic abnormality, laboratory tests (Appendix 6, Section 10.6), including ALT, AST, ALP, TBL, D. Bil, GGT, and CK, should be repeated within 48 to 72 hours to confirm the abnormality, and to determine if it is increasing or decreasing if 1 or more of these conditions occur:

If a participant with baseline results of...	develops the following elevations:
ALT or AST <1.5x ULN	ALT or AST ≥3x ULN
ALP <1.5x ULN	ALP ≥2x ULN
TBL <1.5x ULN	TBL ≥2x ULN (except for patients with Gilbert's syndrome)
ALT or AST ≥1.5x ULN	ALT or AST ≥2x baseline
ALP ≥1.5x ULN	ALP ≥2x baseline
TBL ≥1.5x ULN	TBL ≥2x baseline (except for patients with Gilbert's syndrome)

If the abnormality persists or worsens, clinical and laboratory monitoring and evaluation for possible causes of abnormal liver tests should be initiated by the investigator in consultation with the Lilly-designated medical monitor. At a minimum, this evaluation should include physical examination and a thorough medical history, including symptoms, recent illnesses (for example, heart failure, systemic infection, hypotension, or seizures), recent travel, history of concomitant medications (including over-the-counter), herbal and dietary supplements, history of alcohol drinking, and other substance abuse.

Initially, monitoring of symptoms and hepatic biochemical tests should be done at a frequency of 1 to 3 times weekly, based on the participant's clinical condition and hepatic biochemical tests. Subsequently, the frequency of monitoring may be lowered to once every 1 to 2 weeks, if the participant's clinical condition and lab results stabilize. Monitoring of ALT, AST, ALP, and TBL should continue until levels normalize or return to approximate baseline levels.

Comprehensive hepatic evaluation

A comprehensive evaluation should be performed to search for possible causes of liver injury if 1 or more of these conditions occur:

If a participant with baseline results of...	develops the following elevations:
ALT or AST <1.5x ULN	ALT or AST ≥ 3 x ULN with hepatic signs/symptoms*, or ALT or AST ≥ 5 x ULN
ALP <1.5x ULN	ALP ≥ 3 x ULN
TBL <1.5x ULN	TBL ≥ 2 x ULN (except for patients with Gilbert's syndrome)
ALT or AST ≥ 1.5 x ULN	ALT or AST ≥ 2 x baseline with hepatic signs/symptoms*, or ALT or AST ≥ 3 x baseline
ALP ≥ 1.5 x ULN	ALP ≥ 2 x baseline
TBL ≥ 1.5 x ULN	TBL ≥ 1.5 x baseline (except for patients with Gilbert's syndrome)

*Hepatic signs/symptoms are severe fatigue, nausea, vomiting, right upper quadrant abdominal pain, fever, rash, and/or eosinophilia >5%.

At a minimum, this evaluation should include physical examination and a thorough medical history, as outlined above, as well as tests for PT-INR; tests for viral hepatitis A, B, C, or E; tests for autoimmune hepatitis; and an abdominal imaging study (for example, ultrasound or CT scan).

Based on the patient's history and initial results, further testing should be considered in consultation with the Lilly-designated medical monitor, including tests for HDV, CMV, EBV) acetaminophen levels, acetaminophen protein adducts, urine toxicology screen, Wilson's disease, blood alcohol levels, urinary ethyl glucuronide, and serum phosphatidylethanol. Based on the circumstances and the investigator's assessment of the participant's clinical condition, the investigator should consider referring the participant for a hepatologist or gastroenterologist consultation, magnetic resonance cholangiopancreatography, endoscopic retrograde cholangiopancreatography, cardiac echocardiogram, or a liver biopsy.

Additional hepatic data collection (hepatic safety CRF) in study participants who have abnormal liver tests during the study

Additional hepatic safety data collection in hepatic safety CRFs should be performed in study participants who meet 1 or more of the following 5 conditions:

1. Elevation of serum ALT to ≥ 5 x ULN on 2 or more consecutive blood tests (if baseline ALT <1.5x ULN)
 - In participants with baseline ALT ≥ 1.5 x ULN, the threshold is ALT ≥ 3 x baseline on 2 or more consecutive tests
2. Elevated TBL to ≥ 2 x ULN (if baseline TBL <1.5x ULN) (except for cases of known Gilbert's syndrome)
 - In participants with baseline TBL ≥ 1.5 x ULN, the threshold should be TBL ≥ 2 x baseline
3. Elevation of serum ALP to ≥ 2 x ULN on 2 or more consecutive blood tests (if baseline ALP <1.5x ULN)

- In participants with baseline ALP $\geq 1.5 \times$ ULN, the threshold is ALP $\geq 2 \times$ baseline on 2 or more consecutive blood tests

4. Hepatic event considered to be an SAE

Note: the interval between the 2 consecutive blood tests should be at least 2 days.

8.2.6. Injection Site Reaction Assessment

Injection site assessments using the ISR CRF, VAS if required (see below), and an exploratory tool (Scarletred) will be performed at times specified in the SoA (Section 1.3).

Injection site pain assessments are part of the solicited and spontaneous ISR assessments. The baseline assessment, and all positive responses of pain from then on, will require an additional assessment using the Pain VAS.

As there are multiple injections for each dose, ISR assessments will be done for each injection. Manifestations of a local ISR may include erythema, induration, pain, pruritus, and edema. Injection site findings will be captured on the eCRF.

Injection site reactions, if recorded as a result of the prespecified (or solicited) assessment, will be recorded as AEs only if they qualify as SAEs.

If a spontaneous (or unsolicited) ISR is reported by a participant or investigator, the ISR CRF will be used to capture additional information about this reaction (for example, degree and area of erythema) at additional visits until resolution of the event.

The VAS is a well-validated tool (Williamson and Hoggart 2005) to assess injection site pain; it is presented as a 100-mm line anchored by verbal descriptors, usually “no pain” and “worst imaginable pain.” The participant will be asked to rate any pain at the injection site on a scale of 0 to 100 on the line, as soon as possible following each injection.

In addition, the exploratory tool (Scarletred) will be used to acquire exploratory ISR data at each of the time points where the ISR data is being collected by administration of the ISR CRF. Failure to take this assessment at any of the indicated time points will not result in a protocol deviation.

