6.6.3. Temporary Stopping Criteria

Dosing will be temporarily halted, and no further participants will be dosed until safety data available at that point have been reviewed:

- 3 or more participants develop AEs that are graded as at least moderate, considered related to study treatment, clinically significant, and not responsive to supportive care.
- if 1 or more participants develop AEs related to study treatment and that are serious (SAEs) or graded as severe.

This table describes the location of AE-related information in this protocol.

Topic	Location
Definition of AEs	Section 10.3.1
Assessment of Intensity/Severity	Section 10.3.3

Changes to the planned dosing schedule must be appropriately documented and communicated with the study personnel and the IRB/IEC before dosing continues.

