10.3.1. Definition of AE

AE Definition

An AE is any untoward medical occurrence in a clinical study participant temporally associated with the use of study intervention, whether or not considered related to the study intervention.

NOTE: An AE can therefore be any unfavorable and unintended sign (including an abnormal laboratory finding), symptom, or disease (new or exacerbated) temporally associated with the use of study intervention.

Events Meeting the AE Definition

- Any abnormal laboratory test results (hematology, clinical chemistry, or urinalysis) or other safety assessments (for example, ECG, radiological scans, vital signs measurements), including those that worsen from baseline, considered clinically significant in the medical and scientific judgment of the investigator (i.e., not related to progression of underlying disease).
- Exacerbation of a chronic or intermittent pre-existing condition including either an increase in frequency and/or intensity of the condition.
- New conditions detected or diagnosed after study intervention administration even though it may have been present before the start of the study.
- Signs, symptoms, or the clinical sequelae of a suspected drug-drug interaction.
- Signs, symptoms, or the clinical sequelae of a suspected overdose of either study intervention or a concomitant medication. Overdose per se will not be reported as an AE/SAE unless it is an intentional overdose taken with possible suicidal/self-harming intent. Such overdose should be reported regardless of sequelae.

Events NOT Meeting the AE Definition

- Lack of drug effect is not an AE in clinical studies, because the purpose of the clinical study is to establish treatment effect.
- The following study-specific clinical events related to COVID-19 are exempt from AE reporting unless the investigator deems the event to be related to the administration of intervention:
 - Hypoxemia due to COVID-19 requiring supplemental oxygen;
 - Hypoxemia due to COVID-19 requiring non-invasive ventilation or high flow oxygen devices;

- Respiratory failure due to COVID-19 requiring invasive mechanical ventilation or ECMO
- Any clinically significant abnormal laboratory findings or other abnormal safety assessments which are associated with the underlying disease under study, unless judged by the investigator to be more severe than expected for the participant's condition.

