10.3.2. Definition of SAE

Please note: If an event is not an AE per definition above, then it cannot be an SAE.

An SAE is defined as any AE that:

a. Results in death

b. Is immediately life-threatening

The term 'life-threatening' in the definition of 'serious' refers to an event in which the participant was at risk of death at the time of the event. It does not refer to an event, which hypothetically might have caused death, if it were more severe.

c. Requires inpatient hospitalization or prolongation of existing hospitalization

- In general, hospitalization signifies that the participant has been admitted to hospital for > "23 hour observation" and/or treatment that would not have been appropriate in the physician's office or outpatient setting. Complications that occur during hospitalization are AEs. If a complication prolongs hospitalization or fulfills any other serious criteria, the event is serious. When in doubt as to whether "hospitalization" occurred or was necessary, the AE should be considered serious.
- Hospitalization for elective treatment of a pre-existing condition that did not worsen from baseline is not considered an AE.

d. Results in persistent disability/incapacity

- The term disability means a substantial disruption of a person's ability to conduct normal life functions.
- This definition is not intended to include experiences of relatively minor medical significance such as uncomplicated headache, nausea, vomiting, diarrhea, influenza,

and accidental trauma (for example, sprained ankle) which may interfere with or prevent everyday life functions but do not constitute a substantial disruption.
e. Is a congenital anomaly/birth defect
f. Other situations: 
• Medical or scientific judgment should be exercised in deciding whether SAE reporting is appropriate in other situations such as important medical events that may not be immediately life-threatening or result in death or hospitalization but may jeopardize the participant or may require medical or surgical intervention to prevent one of the other outcomes listed in the above definition. These events should usually be considered serious.
○ Examples of such events include intensive treatment in an emergency room or at home for allergic bronchospasm, blood dyscrasias or convulsions that do not result in hospitalization, or development of drug dependency or drug abuse.

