10.3.3. Recording and Follow-Up of AE and/or SAE

AE and SAE Recording

When an AE/SAE occurs, it is the responsibility of the investigator to review all documentation (for example, hospital progress notes, laboratory reports, and diagnostics reports) related to the event.

The investigator will then record all relevant AE/SAE information in the CRF.

It is not acceptable for the investigator to send photocopies of the participant's medical records to Sponsor or designee in lieu of completion of the AE/SAE CRF page.

There may be instances when copies of medical records for certain cases are requested by Sponsor or designee. In this case, all participant identifiers, except the participant number, will be redacted on the copies of the medical records before submission to Sponsor or designee.

The investigator will attempt to establish a diagnosis of the event based on signs, symptoms, and/or other clinical information. Whenever possible, the diagnosis (not the individual signs/symptoms) will be documented as the AE/SAE.

Assessment of Intensity/Severity

The investigator will make an assessment of intensity for each AE and SAE reported during the study and assign it to one of the following categories, which together with serious criteria on the AE CRF ("results in death" and "life-threatening"), are aligned with the Division of AIDS Table for Grading the Severity of Adult and Pediatric Adverse Events, version 2.1 (DAIDS 2017).

Mild: Mild symptoms causing no or minimal interference with usual social and functional activities, with intervention not indicated.

Moderate: Moderate symptoms causing greater than minimal interference with usual social and functional activities, with intervention indicated.

Severe: Severe symptoms causing inability to perform usual social and functional activities, with intervention or hospitalization indicated.

An event is defined as 'serious' when it meets at least 1 of the predefined outcomes as described in the definition of an SAE, NOT when it is rated as severe.

Assessment of Causality

The investigator is obligated to assess the relationship between study intervention and each occurrence of each AE/SAE.

A "reasonable possibility" of a relationship conveys that there are facts, evidence, and/or arguments to suggest a causal relationship, rather than a relationship cannot be ruled out.

The investigator will use clinical judgment to determine the relationship.

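### Section 8.2.6 keeps non-serious solicited injection site reactions out of AE recording, so whether a severe one triggers the 6.6.3 halt is unclear; separately, SoA footnote c acts on Day 29 although scheduled checks end on Day 7

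*Protocol*

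**What the plan says.** **Recording.** Protocol 8.2.6 separates two routes. ISRs picked up by the planned assessments "will be recorded as AEs only if they qualify as SAEs". For an ISR raised spontaneously by the participant or investigator, 8.2.6 sets no such limit; the ISR form then collects extra detail at additional visits until the reaction resolves.

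**Halting.** Protocol 6.6.3 has two criteria, both written in terms of AEs. The first is "3 or more participants develop AEs that are graded as at least moderate, considered related to study treatment, clinically significant", with the added condition that the event has not responded to supportive care. The second is "if 1 or more participants develop AEs related to study treatment and that are serious (SAEs) or graded as severe". For definitions, 6.6.3 says "This table describes the location of AE-related information in this protocol" and points to 10.3.1 for what an AE is and to 10.3.3 for severity.

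**Grading.** Protocol 10.3.3 attaches both judgements to AEs and SAEs: "The investigator will make an assessment of intensity for each AE and SAE reported during the study" and "The investigator is obligated to assess the relationship between study intervention and each occurrence of each AE/SAE". It also states that a severe rating does not make an event serious.

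**Follow-up of ISRs.** The injection-site row of the SoA (Protocol 1.3) has entries from Day 1 to Day 7 and is blank for Days 15, 29, 60 and 85. Footnote c calls for further assessments at later visits if an ISR persists on Day 29, and for an assessment at an early discontinuation visit if an ISR is present then.

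**The concern.** Criterion 2 makes an event that is severe but not serious a halt trigger in its own right. Section 8.2.6 takes that same category out of AE recording when the event is an ISR found by a planned check. Two careful readers could then reach different halt decisions on the same reaction, depending on who mentioned it first. Criterion 1 has the same ambiguity for moderate reactions.

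ISRs are a named risk of SC injection (Protocol 2.3), this is the first SC use of the formulation (4.2), and 6.6.3 is the only section that sets out halt criteria. What is at stake is whether later participants in a cohort are dosed before the data are reviewed. This matters most in Cohort 2, which receives the larger volume and has no later escalation review behind it.

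The footnote c point is separate and smaller: the protocol gives an instruction that depends on an observation it does not schedule.

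**Working it through.** The plan states no figure on this point, so the check sets the sections side by side and then does the day arithmetic.

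**1. The same reaction by two routes.** Take an ISR that is severe, related and not serious.

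| Step | Found at a planned check | Raised spontaneously |
|---|---|---|
| AE record | Withheld by 8.2.6 | Not restricted by 8.2.6; the general duty in 8.3 and 8.3.1 applies |
| 10.3.3 grade and causality call | No stated route | As for any AE |
| 6.6.3, criterion 2 | Unclear | Met |

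ISR severity is part of an exploratory endpoint (Protocol 3), so some severity measure is collected. Nothing ties that measure, or the pain VAS, to the 10.3.3 scale or to 6.6.3. Nor does the protocol say whether an ISR first found at a planned check becomes a recordable AE if the participant mentions it later at AE review.

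**2. The definitions.** Section 10.3.1 says "An AE is any untoward medical occurrence in a clinical study participant temporally associated with the use of study intervention", and ISRs are not among the events it excludes. Section 10.3.2 adds "If an event is not an AE per definition above, then it cannot be an SAE". Since 8.2.6 allows a solicited ISR to be an SAE, such an ISR must be able to be an AE. The definitions therefore pull towards counting it, while the recording rule removes the record on which the count would rest.

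**3. Where the escalation review helps and where it does not.** Section 6.6.1 names AEs and vital signs, then brings everything available from Cohort 1 into the review. That can reach ISR data before Cohort 2 starts. It does not settle whether the 6.6.3 trigger is met within Cohort 2. The injection load by cohort is:

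- Cohort 1: 350 mg ÷ 125 mg/mL = 2.8 mL = 2 × 1.4 mL
- Cohort 2: 1000 mg ÷ 125 mg/mL = 8.0 mL = 4 × 2.0 mL

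**4. Footnote c.** Laying the injection-site row against the SoA column headings puts entries on Days 1 to 7 only. The PK row read the same way gives 11 samples, which matches the 11 in Protocol 10.2.1, so the column reading is sound.

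- Scheduled ISR checks at follow-up visits (Days 15, 29, 60, 85): 0 of 4
- Last check to footnote trigger: 29 − 7 = 22 days; with the ±3-day window, 26 − 7 = 19 to 32 − 7 = 25 days
- If the trigger were Day 7, next existing visit: 15 − 7 = 8 days; with the ±2-day window, 13 − 7 = 6 to 17 − 7 = 10 days

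**The case against.** The best reply is that 6.6.3 turns on what participants develop, whereas 8.2.6 governs only what is written down. By 10.3.1 and 10.3.2 an ISR is already an AE, so on a plain reading a severe related ISR counts however it was found. Other text narrows the gap further. AEs are collected from consent to the end of participation (8.3.1), and the investigator must record events that meet the AE definition (8.3). The investigator can personally raise a spontaneous ISR (8.2.6), data are evaluated on an ongoing basis (6.6.1), a few unblinded sponsor staff can see safety data (6.6.2), and immediate safety concerns go to the sponsor at once (Section 8). Participants are inpatients to Day 7. Severe under 10.3.3 means unable to carry out usual activities, which is hard to overlook. Keeping solicited reactions out of AE tables is also a legitimate choice.

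Most of this stands, and it limits the point to an ambiguity. It does not remove the point: none of these provisions says whether the criterion is met, and the duty to record in 8.3 conflicts with the instruction in 8.2.6.

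Four stronger readings might be inferred, and the documents do not support them:

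- *A severe solicited ISR cannot halt dosing.* The AE definition allows it to count.
- *The Day 1 schedule creates a measurable delay.* Four planned post-dose checks per injection fall before the first post-dose AE review on Day 2 (4 × 2 = 8 in Cohort 1, 4 × 4 = 16 in Cohort 2). These are only timepoints multiplied by injections. AE collection is continuous, so they measure no delay.
- *ISR data are lost.* SAP 9.4.9 tabulates ISRs and VAS by treatment.
- *An ISR on Day 29 would go unseen.* AE review takes place at all four follow-up visits, examination is available as needed, and spontaneous ISRs are followed to resolution. What is missing is a scheduled ISR check.

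**Conclusion.** The point holds as an ambiguity in the halt rule plus a mismatch in the SoA. A severe, related, non-serious ISR found at a planned check can be argued to trigger 6.6.3. Followed literally, however, 8.2.6 leaves the rule without the record, grade and causality call it needs, so the outcome can depend on the route of detection.

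The affected set is small: the reaction must be severe, not serious, not raised spontaneously by participant or investigator, and must occur while doses in that cohort are still to be given. The documents do not say how dosing is spread within a cohort, and they give no ISR rate, so neither the chance of a missed halt nor the added chance of a halt can be calculated. The ISR form is not in the documents; that it lacks a 10.3.3 grade and a relatedness item is an assumption.

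The footnote c mismatch is certain from the SoA (0 of 4 follow-up visits with a scheduled check, 22 days from last check to trigger) but minor. The primary PK endpoints are untouched. Both changes are worth making because they are cheap.

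**What to change.** (a) In 6.6.3, state that ISRs count toward the halt criteria whether solicited or spontaneous, graded and assessed for causality under 10.3.3. Keep every existing condition of each criterion, including clinical significance and lack of response to supportive care in the first; otherwise three transient moderate reactions could stop dosing. Non-serious solicited ISRs may stay out of the AE tables.

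(b) Change footnote c so that an ISR present on Day 7 is assessed at each later existing visit until it resolves, or add ISR checks at the Day 15 and Day 29 visits.

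Naming ISR data beside AEs and vital signs in 6.6.1 is optional tidying, since that section already covers all Cohort 1 data.

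Cost: a few sentences of protocol text, a grade and causality call for ISRs that could meet a criterion (perhaps an added field on the ISR form), and a few minutes at existing visits. No new visit is needed. The downside is a somewhat higher chance of a temporary halt. It cannot be quantified without an ISR rate, and it leads to a data review, not to the end of the study.
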